4.1 Study Schema

[figure not shown]

Figure 1: Study design with cases (PLWHIV & COVID-19) and two matched control groups.

In total, 500 cases and up to 2500 controls will be analysed.

Only real-world retrospective data will be used for this study. Deidentified retrospective data will be transcribed into the eCRF system from source data at each clinical site or from existing COVID-19 cohort databases, where appropriate.

For comparing PLWHIV & COVID-19 versus HIV seronegative COVID-19 patients, a 1:1 and 1:3 matching will be performed according to the following criteria:

- Age (+/- 5 years)
- Sex
- Ethnicity (where available)
- Month of COVID-19 diagnosis (+/- 2 months)
- COVID-19 diagnosis inpatient, 1:1 matching
OR
- COVID-19 diagnosis outpatient (ambulatory), 1:3 matching

For comparing PLWHIV & COVID-19 versus PLWHIV without COVID-19, a 1:2 matching for similar risk of acquiring COVID-19 will be performed according to the following criteria:

- Age (+/- 5 years)
- Sex
- Ethnicity (where available)

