7.3.2 Primary outcome analysis

The first primary outcome analysis will be performed on PLWHIV with COVID-19 versus HIV uninfected individuals with COVID-19. The endpoint is the occurrence of critical care admission (high dependency unit or intensive care unit), mortality in hospital or palliative discharge when discharged from hospital, or mortality at 6 weeks after diagnosis of COVID-19 or at discharge from hospital (where applicable). Kaplan-Meier estimates will be used to estimate the proportion of participants with the primary endpoint events. Unadjusted and adjusted hazard ratios (HR) will be estimated using the Cox proportional hazard model to assess the impact of HIV-infection on the severity of COVID-19. The validity of the proportionality assumption will be assessed and tested. The adjusted variables will be the following (potential confounders): Age (<60 vs 60-64 vs 65-69 vs 70-74 vs ≥75 years); Sex at birth (female vs male); Obesity (BMI>30 kg/m²); and Comorbidities (see appendix 1).

The second primary outcome analysis will be performed within the group of PLWHIV (PLWHIV with COVID-19 versus PLWHIV without COVID-19). The endpoint is to assess factors associated with severe COVID-19 within the group of PLWHIV. Conditional logistic regression models will be used to account for the case-control matching. The following variables will be assessed: Age (<60 vs 60-64 vs 65-69 vs 70-74 vs ≥75 years); Sex at birth (female vs male); Obesity (BMI >30 kg/m²); Comorbidities (see appendix 1); time since HIV diagnosis (years); current ART; CDC disease stage; CD4 cell nadir; last CD4 cell count/HIV-RNA before COVID-19 diagnosis (including CD4% and CD4/CD8 ratio) at baseline. For continuous variables, the decision to treat the variable as a continuous or categorical variable (as tertile) will be based on the lowest Akaike information criterion value for the corresponding univariable conditional logistic regression analysis. Variables achieving P < 0.20 in the univariable analysis will be retained for the multivariable analysis.

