7.4 Subject population

All eligible subjects with a matching individual will be included in the analysis population (full population analysis).

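### The second primary analysis assesses sex and age in sets matched on sex and age, and its contrast of COVID-19 with no COVID-19 never compares severe with non-severe cases

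*Combined protocol and SAP*

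**What the plan says.** Section 4.1 sets the matching for the HIV-only control group: "a 1:2 matching for similar risk of acquiring COVID-19 will be performed according to the following criteria", namely age within 5 years, sex, and ethnicity where available. No tolerance is given for sex.

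Section 7.3.2 defines the analysis: "The second primary outcome analysis will be performed within the group of PLWHIV (PLWHIV with COVID-19 versus PLWHIV without COVID-19"). Its target is then stated: "The endpoint is to assess factors associated with severe COVID-19 within the group of PLWHIV". The model follows: "Conditional logistic regression models will be used to account for the case-control matching". The candidate factors open with "The following variables will be assessed: Age (<60 vs 60-64 vs 65-69 vs 70-74", then the oldest age band and sex at birth, followed by obesity, comorbidities and HIV-related variables. Variables with P < 0.20 in univariable models go forward to the multivariable model.

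On who is analysed, section 7.4 says: "All eligible subjects with a matching individual will be included in the analysis population". Section 7.3 says the same.

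The target is described in two ways. Primary objective 2 (section 3.1), the second hypothesis in section 7.3 and the endpoint sentence in 7.3.2 all concern severe COVID-19 among PLWHIV. The sample-size paragraph in 7.1 and the last sentence of the introduction to 7.3 describe factors for SARS-CoV-2 infection or for COVID-19 itself. No model restricted to the cases is described anywhere.

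**The concern.** There are two faults in one primary analysis.

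First, matching removes the contrast in the matched variables. A conditional model cannot estimate a factor that is equal within every set. It can estimate a closely matched factor only from the small differences that the caliper leaves. Sex and age are nevertheless listed as factors to assess and screen, and the Rationale (section 2) names both as risk factors for severe illness.

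Second, HIV-only controls have no COVID-19 and so no severity outcome. A contrast of cases with these controls informs who had COVID-19, not who became severely ill. If its results are reported as risk factors for severe COVID-19, primary objective 2 is answered with the wrong quantity. A true driver of severity could be missed, and a driver of infection could be reported in its place.

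**Working it through.** **1. The plan's own figure.** Section 7.1 uses n = 100 + 50i. With 1,500 PLWHIV, i = (1500 − 100)/50 = 28, as stated. This fits the Synopsis (500 cases and 1,000 HIV-only controls). The wording in 7.1, 500 plus 1500 controls, would sum to 2,000 and give (2000 − 100)/50 = 38.

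**2. Sex.** For set i with case 0 and controls 1 and 2, sex s and other covariates x, the conditional likelihood term is

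exp(βx_i0 + γs_i0) / Σ_j exp(βx_ij + γs_ij).

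With s_ij = s_i for all j, exp(γs_i) cancels from numerator and denominator, so the term does not depend on γ. No assumption about the data is needed beyond exact matching. In simulated data (500 cases, 1:2) the within-set sum of squares for sex was 0, no set was discordant, and the fit with sex included returned no standard error.

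**3. Banded age: how many sets carry information.** A set contributes only if its members fall in more than one of the five bands. The documents give no age distribution for the cases, so these inputs are assumptions.

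| Assumption | Sets with more than one band | Sets wholly under 60 |
|---|---|---|
| Mean 45–55, SD 9–13, controls uniform within 5 years of the case | about 7–30% | about 59–92% |
| Source mean 45–55, SD 12, controls sampled from the source, cases older because age raises infection | 21–46% | not computed |

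**4. Age: what is estimated.** Simulation with 500 cases, 1:2 matching, exact sex and a 5-year caliper, drawing from a bell-shaped source (mean 45–55, SD 12):

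- Age ≥60 vs <60: OR 1.2–1.9 in the matched model, against 2.2–4.5 in an unmatched analysis of the same source.
- Continuous age, true OR per 10 years 1.5: matched estimate 1.8–1.9. True OR 2.0: 2.8–2.9. The standard error of the log OR was about 0.25, against 0.05 unmatched.
- With a flat source age distribution, continuous age gave 1.57 and 2.22 for true values of 1.5 and 2.0.

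The caliper is centred on the case, so the continuous estimate depends on the local slope of the source age distribution. The direction of its distortion is therefore not fixed.

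**5. Severity.** Each 1:2 set has one COVID-19 patient, so no set contains both a severe and a non-severe case. Simulated consequence, with about 75 severe cases among 500:

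| Factor | True OR for infection | True OR for severity | Planned matched model | Cases-only logistic model |
|---|---|---|---|---|
| Raises infection only | 1.49 | 1.00 | 1.48–1.54 | 0.92–1.02 |
| Drives severity only | 1.00 | 1.82 | 0.97–1.01 | 1.74–1.90 |

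In the cases-only model sex is estimable: the simulated OR was 1.60–1.75 for a true value of 1.65.

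**6. What a cases-only model can carry.** By the rule in 7.1, (500 − 100)/50 = 8 parameters. The composite's rate in PLWHIV is not given, so a range is shown. The first rate is deaths on the dashboard in section 6.1, 78/1,187 = 6.6%. The next two are the death and ICU rates in 7.1 for people without HIV. The last is an assumption.

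| Rate | Severe events in 500 | Events per parameter at 28 | Events per parameter at 8 |
|---|---|---|---|
| 6.6% | 33 | 33/28 = 1.2 | 33/8 = 4.1 |
| 11% | 55 | 2.0 | 6.9 |
| 15% | 75 | 2.7 | 9.4 |
| 20% | 100 | 3.6 | 12.5 |

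With 75 events, the smallest sex OR detectable at 80% power is about 2.9, 2.4 or 2.15 if 20%, 30% or 40% of cases are women (assumed).

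**The case against.** **The analysis may be meant to study infection.** Section 7.1 and the end of the introduction to 7.3 read that way, and HIV-only controls are then needed. This is fair, but the endpoint sentence in 7.3.2 and primary objective 2 say otherwise, and the sex and age faults remain on either reading.

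**The sex fault shows itself.** A model with sex included returns no usable estimate or P value, so sex cannot pass the screen. The analyst would notice at the first fit. This stands: a reader might infer that the plan would silently report sex as having no effect, and the documents do not support that. The pre-specified step still cannot be carried out.

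**Sex and sex at birth may differ.** Matching is on the first and the model uses the second. If they differ for a few people, sex would be estimated from those few sets only, which is no better.

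**Age bias towards no effect.** A reader might infer that any age effect from this model is pulled towards none. In simulation that held for a real age effect in bands, but continuous age was inflated when the source distribution was bell-shaped. Only distortion can be claimed in general.

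**Lost cases.** A reader might infer that the analysis-population rule discards many hard-to-match cases. The documents do not show this. Section 6.1 reports an estimated 85,279 PLWHIV in care at the dashboard sites, against 1,000 controls needed. Section 7.4 asks for one matching individual and does not say that a case needs a match in both control groups. The loss may be small.

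**Named hypotheses.** Section 3 stresses CD4 count and nadir, and objective 2 adds comorbidities; neither names age or sex. True, but the severity fault in step 5 affects those factors equally.

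**Conclusion.** The point holds. That sex cannot be estimated is algebra, given exact matching. Banded age can be fitted, but only from boundary-straddling sets, about 7–30% of them under assumed age distributions with uniform controls. The result is not a measure of the effect of age. It was attenuated in the simulations with a real age effect, and for continuous age the direction is not fixed.

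The larger consequence is that the planned contrast does not address severity, the stated endpoint of one of the two primary analyses. That follows from the design of the sets; the odds ratios in step 5 only illustrate it. The two descriptions of the model's target contradict each other and must be reconciled.

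The number of cases lost for want of a match cannot be derived from the documents and is not part of the claim. Ethnicity is a matching criterion but is not among the factors that section 7.3.2 assesses, so the estimability fault concerns sex and age only.

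**What to change.** 1. **Severity objective.** In 7.3.2, specify a logistic or Cox model of the severe-outcome composite among all eligible PLWHIV with COVID-19, with age and sex as covariates alongside the HIV-related factors and comorbidities. Section 6.2 lists the component events but not explicitly their dates, which makes logistic regression the simpler choice.
2. **Infection analysis, if kept.** Name it separately as a search for factors associated with COVID-19. Remove sex from its assessed factors. Keep age, as a continuous term, only to adjust for differences left within the caliper, and do not interpret its coefficient.
3. **Wording of the target.** Bring 7.1, 7.3 and 7.3.2 into line with these two analyses.
4. **Analysis population.** Amend 7.3 and 7.4 so that a match is required only for the matched comparisons.

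The cost is SAP wording; the data are already on the collection list in 6.2. The real price is model size. By the plan's own rule 500 cases support 8 parameters, not 28, and Appendix 1 alone lists more than eight comorbidities. The candidate factors for the severity model should therefore be cut to a short pre-specified list, for instance with one comorbidity score in place of separate conditions, and the 28-parameter statement should not be applied to it.

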3. OBJECTIVES AND OUTCOME MEASURES/ENDPOINTS

It is hypothesised that HIV infection is a risk factor for more severe COVID-19 outcomes and that advanced immunodeficiency as defined by current CD4 T-cell count or CD4 T-cell nadir is a risk factor for more severe COVID-19 outcomes in PLWHIV.

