3.1 Primary objective

1. To describe outcomes of COVID-19 in PLWHIV in comparison to HIV seronegative COVID-19 controls.
2. To identify risk factors (e.g. CD4 cell nadir, current CD4 count, co-morbidities) for severe COVID-19 outcomes within the group of PLWHIV.

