7 STATISTICS AND DATA ANALYSIS

7.1 Sample size calculation

The US Veterans Ageing Cohort Study (VACS) reported at AIDS 2020 [20] that the estimated proportion of non-HIV-infected individuals hospitalized with COVID-19 was 35%, 15% in ICU, 8% with invasive mechanical ventilation and 11% died. We anticipate a 1.1 to 2-fold increase in hazard rate in PLWHIV & COVID-19 (cases) relative to HIV-negative & COVID-19 (controls). With 500 cases and 1500 controls, a two-sided log-rank test at an alpha level of 0.05 will achieve at least 80% power to detect a 1.3-fold increase in the hazard rate of hospitalization, 1.4 for ICU, 1.6 for invasive mechanical ventilation and 1.5 for death (refer to Table 1 below). The power calculation was made using the statistical software package nQuery Advanced, with the two samples Log-Rank test module (Version 8.6.1.0).

Table 1

¹ Most recent available after positive SARS-CoV-2 PCR test, up to 10 days after positive test

		Cases (PLWHIV & COVID-19, N=500); Controls (HIV-negative & COVID-19, N=up to 1500) Alpha=5% (two-sided)										
Severity outcome	Outcome (%)	Power (%)										
Hazard Risk		1.1	1.2	1.3	1.4	1.5	1.6	1.7	1.8	1.9	2.0	
Hospitalization	35	20	60	90	99	>99	>99	>99	>99	>99	>99	
ICU	15	11	31	58	81	94	99	>99	>99	>99	>99	
Invasive mechanical ventilation	8	8	19	35	54	73	86	94	98	99	>99	
Death	11	9	24	46	68	85	95	98	>99	>99	>99	

For the search for factors associated with SARS-CoV-2 infection in PLWHIV, the recommended rule of thumb for sample size estimation for multivariable logistic regression models was $n = 100 + 50i$ where i refers to number of independent variables in the final model [34]. With 1500 PLWHIV (500 with COVID-19 and 1500 controls without COVID-19), we would be able to study 28 parameters with sufficient power to produce statistics that are nearly representative of the true values in the targeted population. However, sample size less than 1500 may be sufficient for associations that yield medium to large effect size.

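### The univariable P < 0.20 screen in section 7.3.2 can leave CD4 nadir and last CD4 count, one of the two section 3 hypotheses, without an adjusted estimate

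*Combined protocol and SAP*

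**What the plan says.** Section 3 gives two hypotheses. The first concerns HIV status. The second is that "advanced immunodeficiency as defined by current CD4 T-cell count or CD4 T-cell nadir is a risk factor for more severe COVID-19 outcomes in PLWHIV". Section 3.1 carries the second into primary objective 2: "To identify risk factors (e.g. CD4 cell nadir, current CD4 count, co-morbidities) for severe COVID-19 outcomes within the group of PLWHIV".

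Section 7.3.2 then sets out two primary analyses.

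- **HIV status.** A Cox model with a fixed list of adjustment variables (age, sex, obesity, comorbidities) and no screening step.
- **Factors within people with HIV.** The candidates are age, sex, obesity, comorbidities, time since HIV diagnosis, ART, CDC stage, and "CD4 cell nadir; last CD4 cell count/HIV-RNA before COVID-19 diagnosis (including CD4% and CD4/CD8 ratio) at baseline". On the model: "Conditional logistic regression models will be used to account for the case-control matching". On selection: "Variables achieving P < 0.20 in the univariable analysis will be retained for the multivariable analysis".

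No section exempts the CD4 variables or any confounder from the screen. None says how a CD4 variable that fails it would be reported.

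**The concern.** A variable named in a hypothesis should get an adjusted estimate whatever its unadjusted P value. Here the unadjusted P value decides whether that estimate exists. If CD4 nadir or last CD4 count gives P of 0.20 or more, the multivariable model omits it, and readers cannot tell whether its effect was absent, imprecisely estimated or hidden by confounding.

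The same rule can remove obesity or a comorbidity from the adjustment set, so the CD4 estimates that are reported may be adjusted for a set chosen by chance. The plan does not treat its HIV-status hypothesis this way.

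**Working it through.** **1. The plan's own figure.** Section 7.1 uses n = 100 + 50i. With n = 1,500, i = (1,500 − 100)/50 = 28, which matches "we would be able to study 28 parameters with sufficient power". (The figure fits 500 cases plus 1,000 controls. The 1,500 controls printed in that sentence would make n = 2,000 and i = 38.) Two CD4 variables need 2 parameters if continuous, or 4 if both are tertiles. By the plan's own rule, model size does not require them to be screened.

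**2. The screen's error rate.** Two-sided P < 0.20 means |Z| > 1.2816. With Z ~ N(μ, 1) and μ = log(OR)/SE,

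P(screened out) = Φ(1.2816 − μ) − Φ(−1.2816 − μ).

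This needs no assumption about CD4 if it is expressed through power. A real effect with 80% power at two-sided 0.05 fails the screen 6.4% of the time, with 50% power 25%, and with 30% power 44%.

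**3. Illustrations.** Assumed, because the documents are silent: a binary low-CD4 indicator with 20% or 40% prevalence, and a Wald approximation with SE = √(sum of reciprocal expected 2×2 cells).

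(a) *The contrast as written*, 500 with COVID-19 against 1,000 without, treated as unmatched, with prevalence taken among controls:

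| Prevalence | True OR | Expected cells | SE | μ | Screened out |
|---|---|---|---|---|---|
| 20% | 1.3 | 122.6, 377.4, 200, 800 | 0.131 | 2.01 | 23% |
| 40% | 1.3 | 232.1, 267.9, 400, 600 | 0.111 | 2.38 | 14% |
| 20% | 1.5 | 136.4, 363.6, 200, 800 | 0.128 | 3.17 | 3% |
| 40% | 1.5 | 250, 250, 400, 600 | 0.110 | 3.68 | 1% |

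(b) *Severe versus non-severe among 500 cases*, which section 7.3.2 does not write. Assumed 15% events (75), borrowed from the HIV-negative ICU figure in section 7.1:

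| Prevalence | True OR | Expected cells | SE | μ | Screened out |
|---|---|---|---|---|---|
| 20% | 1.3 | 17.8, 82.2, 57.2, 342.8 | 0.298 | 0.88 | 64% |
| 40% | 1.3 | 34.1, 165.9, 40.9, 259.1 | 0.252 | 1.04 | 59% |
| 20% | 1.5 | 19.5, 80.5, 55.5, 344.5 | 0.291 | 1.39 | 45% |
| 40% | 1.5 | 36.3, 163.7, 38.7, 261.3 | 0.252 | 1.61 | 37% |

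**4. Form of the CD4 variable.** Section 7.3.2 chooses between continuous and tertile coding by AIC. In a simulation of contrast (b) with a linear effect equal to OR 1.5 for the lowest third against the rest, the screen failed in about 25% of runs with continuous CD4 and 39% with a binary split. At OR 1.3 the figures were about 51% and 60%. The rates in (b) are therefore somewhat high if the effect is linear.

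**5. Selection inflation.** Among studies that pass the screen in contrast (a), the geometric mean estimate is about 1.34-1.37 for a true OR of 1.3, and 1.50-1.51 for 1.5. In contrast (b), a true 1.3 averages about 1.6-1.7.

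**6. Masking.** A simulation assumed 500 patients, about 14% events, 20% with low CD4, an adjusted OR of 2.0, and a comorbidity with OR 3 present in 10% of low-CD4 and 40% of other patients. CD4 failed the screen in 59% of runs, and in 20% it failed although its adjusted P was below 0.05. Without that opposing confounding the last figure was 0%.

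**The case against.** Several points on the other side stand.

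- **CD4 is not the sole primary hypothesis.** It belongs to one of two, and section 3.1 names it as an example of the factors sought. The HIV-status hypothesis is not screened.
- **The result is not lost altogether.** A CD4 variable that fails the screen still has its univariable estimate.
- **The large loss rates belong to another analysis.** A reader might take the 37-45% and 59-64% figures as the risk under this plan. They are not: section 7.3.2 writes COVID-19 versus no COVID-19, where moderate effects usually survive.
- **Matching protects age and sex.** A reader might infer that every established confounder can be lost. Section 4.1 matches on sex and on age within 5 years, so the point does not hold for sex and holds only marginally for age. It does hold for obesity and comorbidities.
- **Inflation and masking are conditional.** A reader might conclude that the reported odds ratios are selected for being large. In the written contrast the inflation is small. Masking needs confounding in the opposite direction, and the documents give no evidence of it.

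None of this removes the core point: the rule has no exemption, and it applies to variables that section 3 names in advance.

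**Conclusion.** The concern holds in limited form. Followed as written, section 7.3.2 can leave CD4 nadir or last CD4 count without an adjusted estimate and can drop obesity and comorbidities from the adjustment set. In the 500:1,000 contrast the risk is modest for a weak effect and small at an odds ratio of 1.5. It becomes large only if the analysis is severity among the cases. All these rates rest on the assumed prevalence, coding, event rate and effect sizes, and on ignoring the matching in contrast (a). That the rule permits removal rests on the text alone.

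A separate problem remains. The endpoint is labelled severe COVID-19, but the contrast is COVID-19 versus no COVID-19. Keeping CD4 in that model would not make it a test of severity.

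**What to change.** Amend section 7.3.2 as follows.

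1. Force CD4 nadir, last CD4 count, obesity and a pre-specified comorbidity summary into the multivariable model regardless of univariable P.
2. Report the adjusted estimates and intervals for both CD4 variables whatever their P value.
3. Apply the P < 0.20 screen, if it is kept, only to the remaining exploratory variables.
4. Do not force sex into the matched conditional model: it is constant within each matched set, so its main effect cannot be estimated. Add age and sex only in an unmatched analysis of severity among cases.

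**Cost.** This is a change of SAP wording plus a few degrees of freedom. In the matched model the forced terms take 2-4 parameters for CD4, 1 for obesity and 1 for a single comorbidity score, so 4-6 of the 28 claimed. An analysis of severity among cases would be tighter. Adding age in five bands (4) and sex (1) gives 9-11 parameters, and 75 assumed events gives 75/11 = 6.8 to 75/9 = 8.3 events per parameter before any ART or CDC-stage term. The amendment does not resolve the endpoint and contrast mismatch, which needs its own correction.
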